Table 13. Derivation of Clustered AESI.....	37
Table 14. Partial Date Imputation Rule for AE or Medication	38

List of Figures

Figure 1: Study design flow chart	12
---	----

List of Abbreviations and definitions of terms

Abbreviation	Term
AE	Adverse event
AESI	Adverse event of special interest
ALT	Alanine aminotransferase
ALP	Alkaline phosphatase
AST	Aspartate aminotransferase
ATC	Anatomical Therapeutic Chemical
Ccr	Calculated creatinine clearance
CI	Confidence interval
CR	Complete response
CSR	Clinical study report
CT	Computed tomography
DCR	Disease control rate
DoR	Duration of response
ECG	Electrocardiogram
ECI	Events of clinical interest
ECOG	Eastern Cooperative Oncology Group
EOT	End of treatment
FDA	Food and Drug Administration
FGFR	Fibroblast growth factor receptor
GCP	Good Clinical Practice
ICF	Informed consent form
ICH	International Council for Harmonisation of Technical Requirements
iCPD	Confirmed progressive disease
IgG4	Immunoglobulin G4
IR	Incidence rate
iUPD	Unconfirmed progressive disease
I.V.	Intravenous
mAb	Monoclonal antibody
MedDRA	Medical Dictionary for Regulatory Activities
mg	milligrams
MRI	Magnetic resonance imaging
ms	milliseconds
NCI-CTCAE	National Cancer Institute - Common Terminology Criteria for Adverse Events

NE	Not evaluable
NGS	Next generation sequencing
ORR	Objective response rate
OS	Overall survival
PD	Progressive disease
PD-1	Programmed cell death 1
PD-L1	Programmed cell death ligand 1
PD-L2	Programmed cell death ligand 2
PFS	Progression-free survival
CCI	CCI [REDACTED]
PO	Oral
CCI	CCI [REDACTED]
PR	Partial response
PS	Performance status
PT	Preferred term
Q3W	Every 3 weeks
QD	Once daily
QTcF	Fridericia's corrected QT interval
RECIST	Response Evaluation Criteria in Solid Tumors, Version 1.1
SAE	Serious adverse event
SAP	Statistical Analysis Plan
SD	Stable disease
SI	The International System of Units
SOC	System Organ Class
Tx	Treatment
UC	Urothelial carcinoma
WHO	World Health Organization
WOCBP	Women of childbearing potential

1. INTRODUCTION

The purpose of this statistical analysis plan (SAP) is to describe the planned analyses and data displays to be included in the Clinical Study Report (CSR) for Protocol TAS-120-203.

Pembrolizumab is a potent humanized immunoglobulin G4 (IgG4) monoclonal antibody (mAb) with high specificity of binding to the programmed cell death 1 (PD-1) receptor, thus inhibiting its interaction with programmed cell death ligand 1 (PD-L1) and programmed cell death ligand 2 (PD-L2). Based on preclinical in vitro data, pembrolizumab has high affinity and potent receptor blocking activity for PD-1. Pembrolizumab has an acceptable preclinical safety profile and is in clinical development as an intravenous (I.V.) immunotherapy for advanced malignancies. Pembrolizumab is indicated for the treatment of patients across a number of indications.

Recently published data (Palakurthi et al. 2019) shows that fibroblast growth factor receptor (FGFR) inhibition and anti-PD-1 combination induced significant tumor regression and improved survival. For both erdafitinib monotherapy and combination treatments, tumor control was accompanied by tumor-intrinsic, FGFR pathway inhibition, increased T-cell infiltration, decreased regulatory T cells, and downregulation of PD-L1 expression on tumor cells. Finally, FGFR inhibition may also modulate the microenvironment in non-*FGFR3*-mutated tumors and lead to enhanced efficacy when combined with pembrolizumab in both wild-type and *FGFR3* mutated tumors (Siefker-Radtke et al. 2019).

Futibatinib is a novel and selective small molecule FGFR inhibitor, which is the first irreversible, covalent inhibitor of FGFR1–4 being tested in humans. Futibatinib selectively and irreversibly binds to FGFR to exert an inhibitory effect on the FGF/FGFR pathway. Preclinical studies have shown that futibatinib selectively inhibits the cell growth of human cancer cell lines bearing *FGFR* gene abnormalities; strong antitumor efficacy has been observed with futibatinib in nude mouse or nude rat xenograft models bearing tumors with *FGFR* gene abnormalities.

There is substantial evidence that the combination of a PD-1/PD-L1 inhibitor and an FGFR inhibitor may result in treatment benefit in this population. This Phase 2 study will assess the effect of pembrolizumab and futibatinib on patients with urothelial carcinoma (UC), including patients with *FGFR3* mutation / *FGFR1-4* fusion/rearrangement.

2. STUDY OBJECTIVES AND ENDPOINTS

2.1. Study Objectives

2.1.1. Primary Objective

The primary objective of this study is to assess the antitumor activity of the combination of futibatinib and pembrolizumab in patients with unresectable locally advanced or metastatic UC who are not candidate to receive a platinum-based treatment regimen as measured by objective response rate (ORR).

2.1.2. Secondary Objectives

- To evaluate disease control rate (DCR)
- To evaluate duration of response (DoR)
- To evaluate progression-free survival (PFS)
- To evaluate overall survival (OS)
- To investigate the safety of futibatinib in combination with pembrolizumab

2.1.3. Exploratory Objectives

CC1

CC1

CC1

2.2. Study Endpoints

2.2.1. Primary Endpoint

- ORR, defined as the proportion of patients experiencing a best overall response of partial response (PR) or complete response (CR)

[figure not shown]
2.2.2. Secondary Endpoints

- DCR, defined as the proportion of patients experiencing a best overall response of stable disease (SD), PR, or CR
- DoR, defined as the time from the first documentation of response (CR or PR) to the first documentation of objective tumor progression or death due to any cause, whichever occurs first
- PFS, defined as the time from first dose of study therapy to the date of death (any cause) or disease progression, whichever occurs first
- OS, defined as the time from the date of first dose to the death date
- Safety, based on reported adverse events (AEs) and on-study laboratory parameters, graded according to the National Cancer Institute—Common Terminology Criteria for Adverse Events (NCI-CTCAE), Version 5.0

All the endpoints based on tumor response (ORR, DCR, DoR, PFS) will be calculated based on both Response Evaluation Criteria in Solid Tumors Version 1.1 (RECIST 1.1) and iRECIST criteria (Eisenhauer et al. 2009, Seymour et al. 2017).

2.2.3. Exploratory Endpoints

CCI

CCI

[figure not shown]
CCI

3. STUDY DESCRIPTION

3.1. Summary of Study Design

Study TAS-120-203 is an open-label, non-randomized, multicenter Phase 2 study evaluating the combination of futibatinib and pembrolizumab in patients with advanced or metastatic UC who are not candidates to receive a platinum-based treatment regimen. The design is briefly summarized in Figure 1.

Abbreviations: FGFR=fibroblast growth factor receptor; I.V.=intravenous; mg=milligrams; PD=progressive disease; PO=oral; QD=daily; Q3W=every 3 weeks; Tx=treatment.

Figure 1: Study design flow chart

A treatment cycle is defined as 21 days. All enrolled patients will receive the same treatment regimen:

- Futibatinib at an oral (PO) dose of 20 mg daily (QD); and
- Pembrolizumab at an intravenous (I.V.) dose of 200 mg every 3 weeks (Q3W).

Treatment will continue until disease progression, unacceptable toxicity, or any other of the criteria for treatment discontinuation is met; of note, pembrolizumab may be administered for a maximum of 35 doses or a maximum duration of 2 years, whichever is earlier.

The study will begin with a safety lead-in period. During this period, a total of 6 patients with advanced or metastatic urothelial carcinoma will be enrolled and treated for at least one 21-day cycle. Patients will be enrolled into this initial safety lead-in period without regard for FGFR alteration status.

After the first 6 patients have completed one cycle of treatment, the first safety analysis will occur. After confirmation of the safety of the combination, a total of 20 additional patients will be enrolled into each of the following 2 cohorts:

- Cohort A: Patients with UC and *FGFR3* mutation or *FGFR* fusion/rearrangement. Patients will be enrolled based on local results but tissue samples will be archived for retrospective confirmation at a central lab using next generation sequencing (NGS)
- Cohort B: All other patients with UC (including patients with other *FGFR* or non-*FGFR* aberrations and patients with wild-type [non-mutated] tumors)

A second safety analysis will occur after enrollment of a total of 10 patients (including the 6 patients from the safety lead-in), in order to confirm the safety profile of the combination before proceeding to the enrollment of the remaining patients in Cohorts A and B.

Please note: at each safety interim analysis, the combination of futibatinib and pembrolizumab will be considered intolerable if the incidence of unacceptable toxicity including dose-limiting toxicity (as defined in Section 5.2 “Definition of Dose-Limiting Toxicity” of the protocol) is $\geq 33\%$. If the combination is determined to be intolerable, the study may continue with a reduced dose of futibatinib (16 mg QD) if medically appropriate in the opinion of the investigator and Sponsor.

Of note, the 6 patients initially enrolled in the safety lead-in period will also be assigned to the respective cohort based on *FGFR* alteration, such that each cohort will contain a minimum of 20 and a maximum of 26 patients.

The detailed study schedule is shown in Table 1.

Table 1. Schedule of Events

Evaluations on Day 1 (D1) of a cycle should be performed within 24 hours prior to dosing, unless otherwise noted. Procedures already performed during the screening period within 72 hours prior to dosing do not need to be repeated on Cycle 1D1 (C1D1). The End of Treatment (EOT) visit must be performed 0-7 days after a decision is made to discontinue study treatment (for patients who discontinue at a planned study visit, that visit may be considered the EOT visit if all assessments required at EOT are performed).

Evaluation	Screening (Within 28 days of 1 st dose)	Treatment Period (1 cycle =21 days)					Safety Follow-up	Survival Follow-up Period (every 12±2 weeks)	Notes			
		Cycle 1		Cycle ≥2								
		D1 (-1 day)	D8 (-1 day)	D15 (-1 day)	D1 (-1 day)	End of Cycle (±7days)						
Written informed consent	X									Written informed consent will be obtained prior to any study-related assessments or procedures.		
Review eligibility criteria	X											
Demographics/medical history	X											
Review of baseline signs and symptoms	X											
Prior & concomitant medications, AE assessments							►			Collect from the time main informed consent is signed through 90 days after administration of the last dose of study therapy or until the start of new anticancer therapy, whichever is earlier.		
Physical examination	X	X			X		X	X		Within 24 hours prior to dosing.		
Vital signs	X	X			X		X	X		Heart rate, blood pressure, body temperature, and respiration rate.		
Height and Weight	X	X			X		X	X		Height at screening only.		
ECOG performance status	X	X			X		X	X		Within 24 hours prior to dosing.		
12-Lead electrocardiogram		X			X		X	X				

Evaluation	Screening (Within 28 days of 1 st dose)	Treatment Period (1 cycle =21 days)					Safety Follow-up		Notes	
		Cycle 1		Cycle ≥2						
		D1 (-1 day)	D8 (-1 day)	D15 (-1 day)	D1 (-1 day)	End of Cycle (±7days)	End of Treatment (+0-7 days)	30, 60, and 90 days after last dose (±3 days)		
Hematology	X	X	X	X	X		X	X	Within 24 hours prior to dosing. More frequent assessments may be performed if clinically indicated	
Coagulation	X	X			X		X	X		
Chemistry (serum or plasma)	X	X	X	X	X		X	X		
Thyroid Function Tests	X	X			X				Every 6 weeks until discontinuation of pembrolizumab.	
Pregnancy test	X						X		Serum pregnancy test required within 7 days prior to first dose for WOCBP. Additional testing (urine or serum) as required per local practice.	
Ophthalmological examination	X			See Note					Examination to be performed by an ophthalmologist or qualified delegate. At screening, 4-6 weeks after first dose, and as indicated if symptoms or signs of mineral deposits. In cases of retinal pigment epithelial detachment, events should be monitored at 2-3-week intervals.	
CCI				X					CCI	

Evaluation	Screening (Within 28 days of 1 st dose)	Treatment Period (1 cycle =21 days)					Safety Follow-up		Notes	
		Cycle 1		Cycle ≥2						
		D1 (-1 day)	D8 (-1 day)	D15 (-1 day)	D1 (-1 day)	End of Cycle (±7days)	End of Treatment (+0-7 days)	30, 60, and 90 days after last dose (±3 days)		
Blood sample for CCI assessment		X			X		X		CCI [REDACTED]	
Tumor tissue collection for CCI assessment	X				X				Mandatory tissue collection at baseline (archival or new tumor biopsy). Optional tumor biopsy to be performed at Day 1 of Cycle 2 only .	
Tumor assessments (CT/MRI)	X					(X)	X	X	At baseline and the end of every 3 cycles (±7 days), or as clinically indicated, until radiologic PD or initiation of new anticancer therapy (whichever comes first). For patients who discontinue treatment for reasons other than radiographic disease progression, imaging will be performed at EOT, (if the prior scan was performed ≥9 weeks before EOT) and during Survival Follow-up until radiologic disease progression or initiation of new anticancer therapy (whichever occurs first).	
Survival status								X	For all patients, unless patient withdraws consent or the study is terminated early by the Sponsor.	

3.2. Treatment Assignment and Blinding/Unblinding

After the patient's initial eligibility is established and informed consent has been obtained, futibatinib will be administered orally at a dose of 20 mg daily, and pembrolizumab will be administered as an I.V. infusion of 200 mg on Day 1 of each cycle (that is, every 3 weeks).

This is an open-label, non-randomized study. Blinding/unbinding is not applicable.

3.3. Determination of Sample Size

Approximately 20 patients will be enrolled in Cohort A. Sample size considerations are based on differentiating a historical control ORR per RECIST 1.1 of 35% or less, with a target ORR per RECIST 1.1 of 65%. Assuming the true ORR per RECIST 1.1 is 65%, the cohort has an approximate 80% power to reject the null hypothesis that the true ORR per RECIST 1.1 is $\leq 35\%$, considering a 2-sided alpha of 10%. With a sample size of 20, observing at least 12 responders will have a 90% confidence interval (CI) lower bound excluding 10% (ORR per RECIST 1.1 of 60% with 90% CI (39.4% - 78.3%)).

Approximately 20 patients will be enrolled in Cohort B. Sample size considerations are based on differentiating a historical control ORR per RECIST 1.1 of 25% or less, with a target ORR per RECIST 1.1 of 50%. Assuming the true ORR per RECIST 1.1 is 50%, the cohort has an approximate 80% power to reject the null hypothesis that the true ORR per RECIST 1.1 is $\leq 25\%$, considering a 2-sided alpha of 10%. With a sample size of 20, observing at least 9 responders will have a 90% CI lower bound excluding 10% (ORR per RECIST 1.1 of 45% with 90% CI (25.9% - 65.3%)).

Note that the first 6 patients will be enrolled into the initial safety lead-in period without regard for FGFR alteration status. The 6 patients will also be assigned to Cohorts A or B based on *FGFR* alteration, such that each cohort will contain a minimum of 20 and a maximum of 26 patients.

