17. Has a known psychiatric or substance abuse disorder that would interfere with the participant's ability to cooperate with the requirements of the study.

Evaluation Criteria:

Efficacy

Efficacy parameters will be assessed based on on-site tumor assessments (including computed tomography [CT] or magnetic resonance imaging [MRI] if CT scan is not feasible) performed by the Investigator/local radiologist according to RECIST 1.1 guidelines [[Eisenhauer et al. 2009](#)]). The primary endpoint will be ORR, defined as the proportion of patients experiencing a best overall response of CR or PR.

In addition to RECIST 1.1, iRECIST will be used. iRECIST is based on RECIST 1.1, but adapted to account for the unique tumor response seen with immunotherapeutic drugs. iRECIST will be used by the Investigator to assess tumor response and progression, and make decisions regarding the continuation of study treatment.

When clinically stable, participants should not be discontinued until progression is confirmed by the Investigator, working with local radiology, according to the rules outlined in the protocol. This allowance to continue treatment despite initial radiologic progression takes into account the observation that some

participants can have a transient tumor flare in the first few months after the start of immunotherapy, and then experience subsequent disease response. This data will be captured in the clinical database.

Safety

The assessment of safety will be based on the incidence of treatment-emergent adverse events (TEAEs) and on-study laboratory parameters. Grading of TEAEs will be performed using the NCI-CTCAE, Version 5.0.

CCI

- CCI
- CCI
- CCI

Statistical Methods:

Determination of Sample Size

Approximately 20 patients with UC and FGFR3 mutations or FGFR1-4 fusion/rearrangement will be enrolled in Cohort A. Sample size considerations are based on differentiating a historical control ORR per RECIST 1.1 of 35% or less, with a target ORR per RECIST 1.1 of 65%. Assuming the true ORR per RECIST 1.1 is 65%, the cohort has an approximate 80% power to reject the null hypothesis that the true ORR per RECIST 1.1 is $\leq 35\%$, considering a 2-sided alpha of 10%. With a sample size of 20, observing at least 12 responders will have a 90% confidence interval (CI) lower bound excluding 10% (ORR per RECIST 1.1 of 60% with 90% CI (39.4% - 78.3%)).

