4.3. Populations for Analysis

- **All Enrolled Population:** All patients enrolled in this study
- **All Treated Population/Full Analysis Set:** All patients in the All Enrolled Population who received at least one dose of study drug. Unless otherwise specified, the All Treated Population will be the basis for the summaries of efficacy and safety.

■ CCI

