5.4.1. Primary Efficacy Analyses

The primary endpoint is ORR per RECIST 1.1. The description of each efficacy endpoint is provided in Table 3. Tumor assessments will be performed as per Table 1. The evaluation of endpoints will be based on the Investigator or local radiologist.

Table 3. Efficacy Endpoint Definitions

Endpoint	Definition
ORR	The proportion of patients experiencing a best overall response of PR or CR
DCR	the proportion of patients experiencing a best overall response of SD, PR, or CR
DoR	The time from the first documentation of response (CR or PR) to the first documentation of objective tumor progression or death due to any cause, whichever occurs first
PFS	The time from first dose of study therapy to the date of death (any cause) or disease progression, whichever occurs first
OS	The time from the date of first dose to the death date

Abbreviations: ORR=objective response rate; CR=complete response; PR=partial response; SD=stable disease; DCR=disease control rate; DoR=duration of response; OS=overall survival; PFS=progression-free survival

ORR per RECIST 1.1 will be summarized by a binomial response rate for each cohort. ORR per RECIST 1.1 will be calculated based on the best overall response recorded from the start of treatment until progression disease or start of subsequent new anticancer treatment. The overall

response can be derived based on target lesion response, non-target lesion response and the emergence of new lesion for patients with measurable disease at baseline. Table 4 presents the rules to derive the overall response.

The best overall response, CR and PR, will be confirmed with at least 4 weeks intervals of two consecutive time points. A minimum of 6-week interval between initial treatment (first dosing date) and tumor measurement is required for SD. The confirmation rule of the best overall response per RECIST 1.1 is shown in Table 5.

The exact 2-sided 90% CI based on Clopper–Pearson methodology will be derived for ORR.

For Cohort A, the null hypothesis (ORR of 35%) will be rejected if at least 12 responders observed out of 20 patients.

For Cohort B, the null hypothesis (ORR of 25%) will be rejected if at least 9 responders observed out of 20 patients.

Table 4. Overall Response Assessment with Target/Non-target Lesion and New Lesions

Target Lesions	Non-target Lesions	New Lesions	Overall Response
CR	CR	No	CR
CR	Non-CR/Non-PD or Not all evaluated	No	PR
PR	Non-PD or Not all evaluated	No	PR

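### Exact power at 20 patients is 76.2% (Cohort A) and 74.8% (Cohort B), not about 80%, and the printed rejection counts cover 20 patients only although cohorts will hold 20 to 26

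*SAP*

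**What the plan says.** SAP 3.3 sizes each cohort at approximately 20 patients, with a 2-sided alpha of 10%. Cohort A is set up to distinguish a response rate of 65% from a historical 35%, and Cohort B 50% from 25%. For Cohort A: "Assuming the true ORR per RECIST 1.1 is 65%, the cohort has an approximate 80% power to reject the null hypothesis". The same power is claimed for Cohort B. The Protocol synopsis and Protocol 11.1 carry the same text.

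SAP 5.4.1 gives the decision rule as counts. The Cohort A rule is that "the null hypothesis (ORR of 35%) will be rejected if at least 12 responders observed out of 20 patients". Its counterpart in Cohort B uses a count of 9 out of 20 against a null of 25%. The same section specifies a Clopper–Pearson interval at the 90% level for the primary endpoint.

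On cohort size, SAP 3.1 says that after the six-patient lead-in "a total of 20 additional patients will be enrolled into each of the following 2 cohorts". SAP 3.3 then divides the lead-in patients between the cohorts by their alteration status, with this result: "such that each cohort will contain a minimum of 20 and a maximum of 26 patients". Efficacy is analysed by cohort in the All Treated Population, defined in SAP 4.3 as "All patients in the All Enrolled Population who received at least one dose of study drug".

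**The concern.** There are two connected problems.

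First, the decision rule and interval are exact, but the stated power is not the power of that rule. A reader would take each cohort to have about a one-in-five chance of missing the target effect. Under the printed rule the chance is closer to one in four.

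Second, the counts are tied to a denominator of 20, and the design cannot give 20 in both cohorts at full enrolment. The analyst would have to settle the cut-off after the responses are known, in an open-label study. Using the printed counts with a larger denominator would inflate type I error, and could declare a null rejected while the reported interval still includes it.

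A wording slip adds to this. The sizing text names neither null as the value the lower limit must clear: "With a sample size of 20, observing at least 12 responders will have a 90% confidence interval (CI) lower bound excluding 10" per cent. The Cohort B sentence uses the same 10%.

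**Working it through.** **Inputs.** Nulls 35% (A) and 25% (B), targets 65% and 50%, 2-sided alpha 10% (5% in the upper tail), n = 20: SAP 3.3. Cut-offs 12 and 9, exact interval: SAP 5.4.1. Twenty added per cohort plus six lead-in patients: SAP 3.1 and 3.3.

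**Step 1: reproduce the printed intervals and cut-offs.** The Clopper–Pearson 90% interval is 39.4% to 78.3% for 12/20 and 25.9% to 65.3% for 9/20. Both match SAP 3.3, and their lower limits clear 35% and 25%. One responder fewer fails the 5% tail:

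- A: P(X ≥ 12 | 20, 0.35) = 0.0196; P(X ≥ 11 | 20, 0.35) = 0.0532.
- B: P(X ≥ 9 | 20, 0.25) = 0.0409; P(X ≥ 8 | 20, 0.25) = 0.1018.

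So 12 and 9 are the correct exact cut-offs at n = 20.

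**Step 2: power of those rules.**

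- A: P(X ≥ 12 | 20, 0.65) = 0.7624, or 76.2%; 80 − 76.2 = 3.8 points.
- B: P(X ≥ 9 | 20, 0.50) = 0.7483, or 74.8%; 80 − 74.8 = 5.2 points.

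**Step 3: could a normal approximation explain 80%?** Without continuity correction, power = Φ{[(p1 − p0)√n − 1.645√(p0(1 − p0))] / √(p1(1 − p1))}.

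- A: (0.30 × 4.472 − 1.645 × 0.477) / 0.477 = 1.168, giving 87.9%.
- B: (0.25 × 4.472 − 1.645 × 0.433) / 0.5 = 0.812, giving 79.1%.

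This may explain the Cohort B figure, but not Cohort A. Other variants at the stated alpha give Cohort A 82.5% (continuity-corrected), 86.0% (arcsine) and 87.8% (score, Wald or mid-p cut-off of 11).

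**Step 4: cohort sizes.** With k lead-in patients in A, nA = 20 + k and nB = 26 − k, which sum to 46. The larger cohort therefore has at least 23.

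**Step 5: exact cut-off at each size.** The cut-off is the smallest count whose upper tail under the null is at most 5%. This is the same as requiring the exact 90% lower limit to exceed the null. The last two columns give the one-sided type I error if 12 and 9 are carried over unchanged.

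| n | A: cut-off, power | B: cut-off, power | A: error with 12 kept | B: error with 9 kept |
|---|---|---|---|---|
| 20 | 12, 76.2% | 9, 74.8% | 2.0% | 4.1% |
| 21 | 12, 83.8% | 10, 66.8% | 3.1% | 5.6% |
| 22 | 12, 89.3% | 10, 73.8% | 4.7% | 7.5% |
| 23 | 13, 85.8% | 10, 79.8% | 6.8% | 9.6% |
| 24 | 13, 90.6% | 11, 72.9% | 9.4% | 12.1% |
| 25 | 14, 87.5% | 11, 78.8% | 12.5% | 14.9% |
| 26 | 14, 91.7% | 11, 83.7% | 16.2% | 18.0% |

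**Step 6: carry-over by split (A/B, %).** k = 0: 2.0/18.0; k = 1: 3.1/14.9; k = 2: 4.7/12.1; k = 3: 6.8/9.6; k = 4: 9.4/7.5; k = 5: 12.5/5.6; k = 6: 16.2/4.1. Every split exceeds 5% in at least one cohort.

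**Step 7: conflict with the reported interval.** The exact 90% lower limit is 24.5% for 9/21, which does not exceed 25%, and 33.5% for 12/23, which does not exceed 35%.

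**The case against.** The best defence is that the SAP already implies a rule at any size. It states the nulls, the alpha and an exact 90% interval, so a statistician would reject when the lower limit exceeds the null. On that reading the carry-over error rates describe a misreading of the plan. The Protocol also says that efficacy will be summarised descriptively. This stands in part: the interval method is sound, and the carry-over rates are conditional on a practice the SAP does not prescribe. But SAP 5.4.1 states formal rejection only as counts out of 20, and it does not say that the lower limit decides at other sizes.

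On power, the text speaks of approximate power and approximately 20 patients, and exact power moves in a sawtooth. In Cohort A it is 81.5% at n = 19, 76.2% at 20 and 83.8% at 21, so 20 is a local low. With re-derived cut-offs, Cohort A exceeds 80% at every size from 21 to 26, and at full enrolment it falls short only if no lead-in patient enters it. That is correct and limits the Cohort A point to n = 20. It does not help Cohort B, which is below 80% at every size from 20 to 25, though close to it at 23 and 25.

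The 10% wording is literally true, since limits of 39.4% and 25.9% do exclude 10%. It is a wording correction only.

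**Conclusion.** The concern holds. Under the SAP's own exact rule at its stated size, power is 76.2% in Cohort A and 74.8% in Cohort B, against a claim of about 80% for each. With exact cut-offs re-derived at each size (a derivation from the 90% interval, not printed in the SAP), Cohort A has 83.8% to 91.7% for 21 to 26 patients. Cohort B stays materially low at 21, 22 and 24 (66.8%, 73.8%, 72.9%) and passes 80% only at 26.

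The missing rule matters more for the analysis than the power figure, because at full enrolment at least one cohort must be larger than the only size covered. The inflated error rates rest on the assumption that 12 and 9 are kept unchanged. Under it, the 5% limit is passed from n = 21 in Cohort B and from n = 23 in Cohort A. The 20-patient cut-offs, intervals and type I error (2.0% and 4.1%) are correct. This should be corrected before the final analysis.

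**What to change.** 1. In the Protocol synopsis, Protocol 11.1 and SAP 3.3, restate power at n = 20 as about 76% for Cohort A and 75% for Cohort B, by exact binomial calculation.
2. In SAP 5.4.1, with a cross-reference from SAP 3.3, state that the null is rejected when the lower limit of the exact 2-sided 90% interval exceeds 35% (Cohort A) or 25% (Cohort B) at the number of patients analysed. Print the cut-offs and power for 20 to 26 patients from the table in the working. Stating the rule through the interval also covers fewer than 20, which can occur because only treated patients are analysed: at n = 19 the cut-offs are 11 (power 81.5%) in A and 9 (67.6%) in B.
3. In the sizing text, replace the 10% that the lower limit is said to exclude with 35% for Cohort A and 25% for Cohort B.

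Keep the 20-patient cut-offs and the printed intervals. The cost is a text correction in three places plus one sentence and one small table in SAP 5.4.1. Enrolment and data collection do not change. Because it adds a decision rule where none is now stated, it should be settled before the final analysis.
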